### 8.6.2 CHANGE IN MONOCULAR PHOTOPIC BCDVA

The change in the monocular photopic BCDVA from Preoperative or from Postop Week 3 will be calculated for each study eye in the modified Safety Population:

The BCDVA change will be presented by lens group at each visit as categorical outcomes of “Increase of 15 letters or more”, “Increase of 10-14 letters”, “Increase of 5-9 letters”, “No change”, “Decrease of 5-9 letters”, “Decrease of 10-14 letters”, and “Decrease of 15 letters or more”. The mean change from the prior visit to the next visit will also be summarized in the same manner.

The listing of BCDVA and the possible reason for BCDVA loss of 10 letters or more (including losses related to LDD treatment) will be provided for the eyes reported with a 10-letter or more loss in BCDVA during the study (i.e. from preoperative visit or previous visit).

[REDACTED]

[REDACTED]

[REDACTED]

[REDACTED]

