#### 1.4 INCLUSION CRITERIA

- Must sign a written Informed Consent Document and be willing to undergo cataract surgery for bilateral implantation of either the LAL or SofPort LI61AO IOL (Bausch + Lomb).
- Must be willing to be randomized to either the LAL group (bilaterally implanted with the LAL and receive light treatments for refractive and presbyopia correction) or the Control group (bilateral implantation with the SofPort LI61AO monofocal IOL).
- Between the ages of 40 and 80 inclusive on the day the first cataract surgery is performed.
- Preoperative keratometric cylinder  $< 0.75$  D in both eyes.
- Cataractous lens changes as demonstrated by best corrected distance visual acuity (BCDVA) of 20/40 or worse with or without a glare source in both eyes.
- Best corrected distance visual acuity projected to be 20/20 or better after cataract removal and intraocular lens (IOL) implantation in both eyes as estimated by potential acuity meter (PAM) or surgeon estimation.
- Clear intraocular media other than cataract in both eyes.
- Willing and able to comply with the requirements for study specific procedures and visits.

- [REDACTED] [REDACTED]
- Able to complete a written questionnaire in English.
- Requires an IOL power within the range available for both the LAL and SofPort LI61AO IOLs.

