### 7.3.2 LIGHT TREATMENT PROCEDURE

#### Subjects randomized to the LAL group

Commencing at the Postop Week 3 [REDACTED] visit (17-24 days post-Fellow eye operative visit), both eyes will receive an [REDACTED]

At the Adjustment #1 visit (3-7 days after the Postop Week 3 [REDACTED] visit), both eyes will receive an adjustment #1 light treatment based on the measured manifest refraction at 4 meters at this visit. Eyes measured with a manifest cylinder of  $\geq 0.50$  D will receive a spherocylindrical light treatment while eyes with  $< 0.50$  D of manifest cylinder will receive a non-astigmatic light treatment.

At the Adjustment #2 visit (3 to 7 days after the Adjustment #1 visit), both eyes will receive an adjustment #2 light treatment also based on the measured manifest refraction at 4 meters at this visit. Eyes measured with a manifest cylinder of  $\geq 0.50$  D will receive a spherocylindrical light

treatment while eyes with  $<0.50$  D of manifest cylinder will receive a non-astigmatic light treatment.

Three to 7 days after the Adjustment #2 light treatment, both eyes will be eligible to receive an adjustment #3 light treatment. If the eye's  $|\text{MRSE}|$  is  $\geq 0.25$  D OR manifest cylinder is measured at  $\geq 0.50$  D, then the eye will receive an adjustment #3 light treatment; otherwise the eye will be eligible to proceed to lock-in #1.

The lock-in #1 light treatment will be performed in the primary eye 3 to 7 days after the subject's final adjustment light treatment followed 3 to 7 days later by the lock-in #2 treatment, if needed. The lock-in #1 treatment will be performed in the fellow eye 3 to 7 days after the final lock-in in the primary eye and after confirmation that there has been no ultraviolet (UV) retinal damage per Sections 7.3.2.1 and 7.3.2.2 followed 3 to 7 days later by lock-in #2, if needed. Subjects in the LAL group will receive [REDACTED], up to three spherocylindrical/non-astigmatic light treatments, and one or two lock-in treatments in each eye.

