### 7.3.2.1 Postponement of Light Treatment Procedure(s)

LDL treatments should be delayed in both eyes if any of the following new symptoms or changes in performance are noted in either study eye;

- Color Vision Testing: Treatment should be delayed if the subject scores worse on Part 2 of the City University Color Test than the Postop Week 3 visit for Tritan evaluation.
- Erythropsia Evaluation: With any score of 2 (red), the treatment should be delayed.
- Best Corrected Distance Visual Acuity: With any loss of BCDVA (unless the cause is known to be non-retinal) of 10 letters or more on an ETDRS (logMAR) chart compared to the Postop Week 3 visit BCDVA, treatment should be delayed.

The subject should return for follow-up visits until the subject's visual assessment of erythropsia is a score of 0 or 1 (indicates the paper looks white or pink), the BCDVA is within 10 letters of the Postop Week 3 visit BCDVA and an equivalent or better score than the Postop Week 3 visit test is measured in the Tritan section of the City University Color Test, at which time the next LDL treatment may be delivered.

- If sutures were utilized at the time of surgery to close the incision wound, light treatments should not commence on the eye until a minimum of 4 weeks after suture removal.
- An eye with an ocular adverse event that could be negatively impacted by light treatment or negatively impact the effectiveness or safety of a light treatment should have light treatments delayed until after the adverse event has subsided. This includes corneal edema and superficial punctate keratitis (SPK) (Grade 3 (moderate) or more severe), retinal conditions including diabetic retinopathy and cystoid macular edema, epithelial defect, endophthalmitis

or any other safety concern that the investigator believes may be negatively impacted by light treatment.

- If an eye is discovered with evidence of premature photopolymerization as evidenced as a zone on the lens surface, the investigator should contact the Sponsor for further instructions. (see Appendix 1 for additional details regarding premature photopolymerization).

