#### Spectral Domain OCT Testing Only

Any visit after the Postop Week 3 visit:

- BCDVA is reduced by 10 letters or more when compared with BCDVA at the Postop Week 3 visit unless the cause of the BCDVA loss is known to be non-retinal.  
**OR**
- An increase in score of more than 1 on Part 2 of the Tritan evaluation (City University Color Test) when compared to the Postop Week 3 visit score.

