The LAL must be implanted following specific surgical procedures. If these procedures are not followed by the surgeon, the lens may become scratched or improperly placed in the eye and may need to be explanted prior to light treatments. In order to perform the lens adjustment or the lens lock-in procedures, the subject's pupil needs to be adequately dilated. If this cannot be accomplished for any reason, additional eye drops, injections into the eye, or surgery may need to be utilized to adequately dilate the pupil. If the pupil cannot be adequately dilated after these types of treatments, the LAL may need to be explanted. An unpredicted change in vision can occur resulting from ocular exposure to daylight or any other UV source before the LAL is locked-in. The light treatments may not improve vision and/or manifest refraction, and the adjustment/lock-in procedure may make vision worse, such that it may be necessary to remove and replace the LAL. Vision loss may be permanent and may not be improved by replacing the LAL. There is a potential risk for UV-induced damage to the eye, including the cornea and retina, which may be permanent. UV light can sometimes cause a reactivation of previous herpes virus infection in the eye. A reactivation of herpes virus can cause scarring of the cornea, blurred vision, eye pain, extreme light sensitivity, permanent loss of vision, and possible need for corneal transplant. Temporary or persistent erythropsia and/or temporary or persistent color vision deficiency may occur. Corneal dryness and corneal abrasions from the lens used for adjustment and lock-in can occur. After the lens adjustment(s) or after the lens lock-in procedures, discomfort, itching and light sensitivity may occur. In cases where a spherocylinder adjustment is performed, it is possible that visual disturbances may occur if the IOL rotates or if the correction is not performed on the correct axis of astigmatism.

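### The 8.6.2 listing of 10-letter BCDVA losses leaves out Postop Week 3 as a reference, so a gradual loss counted in the Week 3 table can have no listed reason

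*Combined protocol and SAP*

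**What the plan says.** Section 8.6.2 sets two reference points for the summary, which covers the modified Safety population: "The change in the monocular photopic BCDVA from Preoperative or from Postop Week 3 will be calculated for each study eye". It continues: "The BCDVA change will be presented by lens group at each visit as categorical outcomes of" letter-change classes, which include a decrease of 10–14 letters and a decrease of 15 or more. It also summarizes the mean change between consecutive visits.

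The section then calls for a listing of BCDVA with the possible reason for the loss, expressly including losses related to LDD treatment. That listing is for eyes "reported with a 10-letter or more loss in BCDVA during the study (i.e. from preoperative visit or previous visit". Postop Week 3 is not named.

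Elsewhere Week 3 is the reference for this size of loss. Under 7.3.2.1, with a BCDVA loss "of 10 letters or more on an ETDRS (logMAR) chart compared to the Postop Week 3 visit BCDVA, treatment should be delayed", unless the cause is known to be non-retinal. The OCT rules in 7.3.2.2 also compare with Week 3, and again do not apply where the cause is known: "unless the cause of the BCDVA loss is known to be non-retinal". Section 8.5.4.11 describes change in monocular photopic BCDVA as a key safety outcome.

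**The concern.** The table and the listing in the same section use different reference points. An eye can fall in a 10-letter loss class of the Week 3 table and have no entry that explains it.

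Neither named reference replaces Week 3, which is the last assessment before light treatment begins. The inclusion criteria (1.4) require "best corrected distance visual acuity (BCDVA) of 20/40 or worse with or without a glare source in both eyes", with 20/20 or better projected after surgery, so the preoperative score is usually a low bar. The previous-visit comparison sees only one interval at a time.

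The reason matters most where the other safeguards do not reach. The OCT trigger is waived when the cause is known to be non-retinal, yet 9.12 includes non-retinal treatment risks: it warns that "the adjustment/lock-in procedure may make vision worse" and names corneal abrasion. In the visible text the Week 3 triggers sit in the LAL light-treatment section only, so Control eyes have no such review.

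**Working it through.** **Inputs from the documents**
- References: preoperative and Week 3 for the table; preoperative and previous visit for the listing (8.6.2).
- Control visits after Week 3: Month 3 and Month 6, so 2 intervals (7.5).
- LAL visits after Week 3: two or three adjustments, "one or two lock-in treatments in each eye", Month 3 and Month 6. That is 2 + 1 + 2 = 5 to 3 + 2 + 2 = 7 intervals per eye.

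**Assumed conversion.** 20/40 = 70 letters and 20/20 = 85 letters.

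**Step 1: the preoperative reference.** An eye going from 70 to 85 at Week 3 must fall to 60 to be 10 letters below preoperative: 85 − 60 = 25 letters lost from Week 3.

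**Step 2: two example paths, preoperative score 70**

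| Path from Week 3 | Loss from Week 3 | Largest single step | Compared with preoperative | In table as ≥10 loss | Listed |
|---|---|---|---|---|---|
| Control: 85, 79, 73 | 12 | 6 | 3 better | Yes | No |
| LAL: 85, 83, 81, 79, 76, 73 | 12 | 3 | 3 better | Yes | No |
| Control: 85, 75, 75 | 10 | 10 | 5 better | Yes | Yes |

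The third row shows the limit of the problem: a loss that falls within one interval is caught.

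**Step 3: a bound that needs no SD.** Let g be the letters by which Week 3 exceeds preoperative, and k the number of intervals. For a steady loss in whole letters, an eye stays unlisted if each step is at most 9 and the total is at most 9 + g. The largest unlisted loss is min(9 + g, 9k).

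| g | LAL, k = 5 to 7 | Control, k = 2 |
|---|---|---|
| 0 | 9 (no gap) | 9 (no gap) |
| 5 | 14 | 14 |
| 10 | 19 | 18 |
| 15 | 24 | 18 |

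**Step 4: how often, under assumed noise.** The documents give no test-retest SD. I simulated 200,000 eyes per setting with independent error on each score, rounded to whole letters, and a true 12-letter loss. The LAL path loses 3, 6, 9 and then 12 letters by Month 3 (5 intervals), so the expected loss stays below the 10-letter delay trigger until light treatment ends. Percentage listed under the current rule at SD 1.5 / 2.5 / 4 letters:

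| True path | g = 5 | g = 10 | g = 15 |
|---|---|---|---|
| LAL, gradual | 20 / 45 / 71 | 0.5 / 16 / 55 | 0.5 / 13 / 49 |
| Control, 6 + 6 | 20 / 44 / 62 | 10 / 32 / 53 | 10 / 32 / 52 |
| Control, all by Month 3 | 89 / 82 / 80 | 88 / 77 / 73 | 88 / 76 / 71 |
| LAL, one step at lock-in | 90 / 85 / 87 | 88 / 77 / 79 | 88 / 77 / 77 |

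With Week 3 added as a reference, the first three rows become 89–96%, 74–88% and 82–96%. With 7 LAL intervals, the gradual-path figures under the current rule stay within 4 points of those for 5.

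**The case against.** **Reading.** If the previous visit meant any earlier visit, Week 3 would be covered. The text does not define the term. However, the singular wording, and the same section's summary of change from one visit to the next, point to consecutive visits. The fix would settle the doubt.

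**Mechanism.** A harm tied to one treatment visit would plausibly show as a step, and the current rule catches most of those (last row of the final table). This stands: the gap concerns gradual loss. It also means the difference between arms is only a tendency. On a like-for-like single step, LAL eyes are listed at least about as often as Control eyes. More LAL visits matter only when the loss is spread over many small steps.

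**Other safeguards.** Every such eye is counted in the Week 3 table. In LAL eyes a 10-letter loss from Week 3 leads to treatment delay and OCT review unless the cause is known to be non-retinal. Ocular adverse events in either arm are documented with an assessment of relationship (9.6, 9.6.1). These reduce the consequence, but none of them puts the eye and its reason into the 8.6.2 listing.

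**Redaction.** Redacted lines follow the sentence, 8.6.3 to 8.6.5 are not visible, and part of the adverse event text is blacked out. A further listing could exist there. The listing sentence itself is complete, and this point concerns that sentence only.

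**Conclusion.** The point holds on the visible text. Section 8.6.2 counts 10-letter losses from Week 3 but does not require a reason for all of them. The bound depends only on the visit schedule and on g. The percentages rest on assumed SDs, loss paths and g, none of which the documents supply. Because eligibility may be met with a glare source, preoperative BCDVA without glare can be better than 20/40, so g will vary between eyes.

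The listing is descriptive, so no effectiveness or safety test changes. The change is still worth making, because the listing is the visible place in 8.6.2 where the reasons for loss on a key safety outcome are reported, including losses due to light treatment.

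**What to change.** In 8.6.2, change the bracket to *(i.e. from the preoperative visit, from Postop Week 3, or from the previous visit)*, apply it to both arms, and add a column to the listing showing which reference triggered each entry.

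The cost is one phrase and a flag, using a change the plan already calculates. Some extra entries will be measurement noise. With no true loss, the simulation adds per 112 primary eyes: none at SD 1.5; about 1–2 LAL and fewer than 1 Control at SD 2.5; about 7–9 LAL and 3 Control at SD 4. At SD 4 the LAL listing rate rises from 22–31% to 29–39% and the Control rate from 9–10% to 12%, so much of that noise is already present under the current rule. The flag lets a reader set these entries apart.

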#### 8.6.6 SUBJECTIVE SYMPTOMS AND COMPLAINTS

For each reported subjective symptom and complaint, number and percent of subjects will be summarized for each severity level of the symptom for the modified Safety population by lens group.

#### 8.6.7 OTHER OCULAR EXAMINATIONS

Slit lamp findings, fundus exam findings, and IOP changes will be summarized descriptively for all eyes in the modified Safety population by lens group. Number of LAL eyes with fundus exam changes from the pre-op and from the Postop Week 3 visit including fundus changes associated with UV exposure will be summarized. In addition, number of LAL eyes with confirmed perimetric observations on at least 2 post light treatment visual field tests that were unnoted at the Postop Week 3 visit will be summarized descriptively.

[REDACTED]

[REDACTED]

[REDACTED]

[REDACTED]

[REDACTED]

[REDACTED]

#### **8.6.9 DISTANCE CORRECTED CONTRAST SENSITIVITY (MESOPIC/PHOTOPIC W AND W/O GLARE)**

The contrast sensitivity (in log units) at each spatial frequency level under each of the four test conditions (photopic with and without glare and mesopic with and without glare) at Postop Month 6 will be summarized by mean, standard deviation, median, minimum, maximum and percentile (0th, 25th, 50th, 75th, and 100th) by eye (primary eyes versus fellow eyes) and lens group (LAL group versus control group) in the modified Safety population. The mean difference in log contrast sensitivity between the two lens groups with a 90% non-parametric confidence interval will also be performed for each spatial frequency. The number and frequency of eyes that can and cannot see the target at 100% contrast for each spatial frequency will be presented. Mesopic contrast sensitivity testing results without glare and with glare will be stratified by measured mesopic undilated pupil size (<3.0 mm, ≥3.0 to ≤4.0 mm, and >4.0 mm).

#### **8.6.10 IOL STABILITY (TILT/DECENTRATION)**

The number of eyes reported with IOL tilt and/or IOL decentration at Postop Week 3 (Control)/Adjustment #1 (LAL), Postop Month 3, and Postop Month 6 will be provided. For eyes reported with IOL tilt and/or IOL decentration, the amount of IOL tilt and/or IOL decentration will be summarized descriptively in the modified Safety population.

#### **8.6.11 WAVEFRONT ABERROMETRY**

The sum of all higher order, non-spherical aberrations (S3+S5+S7) will be used as a clinically important Wavefront Aberrometer outcome. The outcomes at Postop Week 3 and at Postop Month 6 visits will be described by mean, standard deviation, median, minimum, and maximum by eye (primary eyes versus fellow eyes) and lens group (LAL versus Control) in the modified Safety population. In addition, for the LAL primary eye, two separate regression analyses will be performed for both the Postop Month 6 DCIVA logMAR and BCDVA logMAR (Y-axis) on the change in this Wavefront Aberrometer outcome from Postop Week 3 to Postop Month 6 (X-axis) to determine the effect of this Wavefront Aberrometer outcome on the Postop Month 6 DCIVA and BCDVA. The regression analysis will also be performed for the LAL fellow eyes

#### **8.6.12 SECONDARY SURGICAL INTERVENTION (SSI)**

Rates of secondary surgical intervention (IOL exchange, removal, and repositioning) related to the optical properties of the IOL will be reported by lens group (LAL versus Control) in the modified Safety population. The two-sided 95% confidence intervals of these rates will be calculated as well as on the difference in rates. SSIs related to the optical properties of the IOL are defined as an SSI due to subject intolerance of visual symptoms not adequately improved by spectacle correction. All SSIs should include investigator assessment

determining if it is “related” or “not related” to the IOL optical properties.

## **8.7 SEQUENCE OF PLANNED ANALYSES**

### **8.7.1 FINAL ANALYSIS**

When all enrolled subjects have completed or exited the study, the final statistical analyses based on the SAP will be performed.

## **9 ADVERSE EVENTS**

If an adverse event (AE) occurs, the first concern will be the safety and welfare of the subject; treatment should be provided as appropriate for the event. During the study, the Investigator should appropriately treat and follow each AE until it resolves, stabilizes, or it is determined that further improvement is not expected.

### **9.1 ADVERSE EVENT DEFINITIONS**

An adverse event (AE) is any untoward medical occurrence, unintended disease or injury, or untoward clinical signs (including abnormal laboratory findings) in subjects, users, or other persons, whether or not related to the investigational medical device.

Note 1 to entry: This definition includes events related to the investigational medical device or the comparator.

Note 2 to entry: This definition includes events related to the procedures involved.

Note 3 to entry: For users or other persons, this definition is restricted to events related to investigational medical devices.

Unanticipated Adverse Device Effects (UADE) are any serious adverse effect on health or safety or any life-threatening problem or death caused by, or associated with a device, if that effect, problem, or death was not previously identified in nature, severity or degree of incidence in the investigational plan or application (including a supplementary plan or application), or any other unanticipated serious problem associated with a device that relates to the rights, safety, or welfare of subjects.

An investigator will submit to the Sponsor and to the reviewing IRB a report of any UADE occurring during an investigation as soon as possible, but in no event later than 10 working days after the investigator first learns of the effect. The Sponsor will immediately conduct an evaluation of any unanticipated adverse device effect. The results of the evaluation will be reported to FDA and to all reviewing IRB's and participating investigators within 10 working days of the Sponsor becoming aware of the event. Thereafter the Sponsor shall submit additional reports concerning the effect as FDA requests. If a UADE is determined by the Sponsor to present an unreasonable risk to study subjects, all investigations or parts of the investigation presenting that risk will be terminated as soon as possible. Termination will occur not later than 5 working days after this determination is made, and not later than 15

working days after first receiving notice of the event. The investigation will not be resumed without IRB and FDA approval.

All events that the investigator regards as clinically significant should be reported to ensure full reporting of all significant adverse events. [REDACTED]

For more information, contact the Office of the Vice President for Research and Economic Development at [contact] or [[contact]](mailto:[contact]).

For more information, contact the Office of the Vice President for Research and the Office of the Vice President for Student Affairs.

1

1. **What is the primary purpose of the study?** (Please check one box)

1

1000

1

■ XXXXXXXXXX

1

11 of 11

1

11. **What is the primary purpose of the *Journal of Clinical Endocrinology and Metabolism*?**

1

11. **What is the primary purpose of the *Journal of Clinical Endocrinology and Metabolism*?**

1. **What is the primary purpose of the study?** (Please check one box)

Digitized by [contact]

11. **What is the primary purpose of the *Journal of Clinical Endocrinology and Metabolism*?**

11. **What is the primary purpose of the *Journal of Clinical Endocrinology and Metabolism*?**

A 10x10 grid of black bars on a white background. The bars are arranged in a pattern where most cells are black, but some are white, creating a sparse, abstract design. The white cells are located at the following coordinates: (1, 1), (1, 2), (1, 3), (1, 4), (1, 5), (1, 6), (1, 7), (1, 8), (1, 9), (1, 10), (2, 1), (2, 2), (2, 3), (2, 4), (2, 5), (2, 6), (2, 7), (2, 8), (2, 9), (2, 10), (3, 1), (3, 2), (3, 3), (3, 4), (3, 5), (3, 6), (3, 7), (3, 8), (3, 9), (3, 10), (4, 1), (4, 2), (4, 3), (4, 4), (4, 5), (4, 6), (4, 7), (4, 8), (4, 9), (4, 10), (5, 1), (5, 2), (5, 3), (5, 4), (5, 5), (5, 6), (5, 7), (5, 8), (5, 9), (5, 10), (6, 1), (6, 2), (6, 3), (6, 4), (6, 5), (6, 6), (6, 7), (6, 8), (6, 9), (6, 10), (7, 1), (7, 2), (7, 3), (7, 4), (7, 5), (7, 6), (7, 7), (7, 8), (7, 9), (7, 10), (8, 1), (8, 2), (8, 3), (8, 4), (8, 5), (8, 6), (8, 7), (8, 8), (8, 9), (8, 10), (9, 1), (9, 2), (9, 3), (9, 4), (9, 5), (9, 6), (9, 7), (9, 8), (9, 9), (9, 10), (10, 1), (10, 2), (10, 3), (10, 4), (10, 5), (10, 6), (10, 7), (10, 8), (10, 9), (10, 10).

